### 10.2 Primary Endpoint

The primary endpoint, number of oocytes retrieved, will be analysed using a negative binomial regression model with treatment (long GnRH agonist protocol or GnRH antagonist protocol), age

stratum (<35, 35-37, or 38-40 years), and AMH at screening (<15 pmol/L or  $\geq$ 15 pmol/L) as factors. A logarithmic link function will be used for the mean in the model. From this model, the mean difference between the two protocols in number of oocytes retrieved will be estimated, and a 95% CI for the estimate will be calculated using the delta method. The analyses will be done using the multiple imputation method described below.

Age stratum is included as factor in the model since randomisation is stratified by age. AMH at screening is additionally included as a factor since AMH is known to influence the number of oocytes retrieved. Although randomisation is stratified by centre, centre and the interaction between centre and age stratum are not included in the model as all centres may not randomise subjects from all age strata, and therefore the inclusion of the interaction in the model is likely to give empty cells in the analysis. The potential influence of centre differences on the results will instead be investigated in a sensitivity analysis.

For subjects in the FAS who discontinue the trial after randomisation but before start of FE 999049 treatment, the number of oocytes retrieved will be imputed from subjects who started FE 999049 treatment in the same protocol, using the following multiple imputation method:

- First, a negative binomial regression model with age stratum and AMH at screening as factors will be fitted to data from subjects who started FE 999049 treatment for each protocol separately.
- In the second step, 1000 complete datasets will be constructed. For the construction of each complete dataset, a set of parameter values will be sampled from a normal distribution with characteristics determined by the estimated parameters and covariance matrix for the two models in the first step. Missing individual subject data will then be imputed from a negative binomial distribution with the sampled parameters.
- In the third step, each complete dataset will be analysed using the negative binomial regression model described in the first paragraph of this section.
- In the final step, the estimated mean differences and the standard deviations from the 1000 analyses will be combined using Rubin's formula:

$$m_{MI} = \frac{1}{1000} \sum_{i=1}^{1000} m_i, \quad SD_{MI} = \sqrt{\frac{1}{1000} \sum_{i=1}^{1000} SD_i^2 + \left(1 + \frac{1}{1000}\right) \left(\frac{1}{1000 - 1}\right) \sum_{i=1}^{1000} (m_i - m_{MI})^2}$$

Where  $m_i$  and  $SD_i$  are the estimated mean differences and standard deviations for the differences for the 1000 copies of the dataset (derived using the delta method), and  $m_{MI}$  and  $SD_{MI}$  are the pooled estimates.

- The mean difference in number of oocytes retrieved between the long GnRH agonist protocol and the GnRH antagonist protocol will be estimated as  $m_{MI}$ , and the 95% CI for the estimate will be calculated as  $m_{MI} \pm 1.96 * SD_{MI}$ .

The assumption underlying the above imputation procedure is that all randomised subjects could have started FE 999049 treatment, and that their outcome would not have differed in any systematic way from the subjects that started FE 999049 treatment.

For subjects who discontinue the trial after start of FE 999049 treatment but before oocyte retrieval the number of oocytes retrieved will be regarded as zero.

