#### 4 Trial design

This is a randomised, controlled, open label, parallel group, multicentre trial comparing the efficacy and safety of individualised FE 999049 dosing in first cycle patients aged 18-40 years undergoing controlled ovarian stimulation for IVF/ICSI following either a long GnRH agonist protocol or a GnRH antagonist protocol. The trial has been designed to describe potential differences in the mean number of oocytes retrieved with adequate precision.

Subjects will be screened within 90 days prior to randomisation for compliance with the inclusion and exclusion criteria. Randomisation may take place as soon as all eligibility criteria are met. Subjects will be randomised in a 1:1 ratio to controlled ovarian stimulation with FE 999049 in a long GnRH agonist protocol or to controlled ovarian stimulation with FE 999049 in a GnRH antagonist protocol. Randomisation will be stratified by centre and according to age (<35, 35-37 and 38-40 years). The subject will be informed of treatment allocation and when to start treatment by the delegated trial staff.

Subjects randomised to treatment with FE 999049 in the long GnRH agonist protocol will start down-regulation with GnRH agonist (triptorelin acetate, GONAPEPTYL) 0.1 mg/day subcutaneously in the mid-luteal phase (i.e. cycle day 21-24) of their menstrual cycle. Ovarian stimulation with FE 999049 will start after 14 days ( $\pm 1$  day) if the subject has experienced withdrawal bleeding and down-regulation criteria are fulfilled. If down-regulation is confirmed and ovarian stimulation is initiated, treatment with GnRH agonist is continued throughout the stimulation period. If the subject has not experienced withdrawal bleeding after 14 days ( $\pm 1$  day), a urinary pregnancy test is to be performed. If the subject is not pregnant and down-regulation is not confirmed, treatment with GnRH agonist will be continued and stimulation will be postponed until down-regulation is confirmed. Subsequent visit(s) for confirmation of down-regulation will be scheduled according to local practice. If down-regulation is not achieved after 28 days, treatment with GnRH agonist will be stopped and the subject will be withdrawn from the trial.

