#### **4.2 Determination of Sample Size**

The purpose of this trial is to gain clinical experience with the use of FE 999049 when applied in a long GnRH agonist protocol. The trial is descriptive and does not include any hypothesis testing. The sample size is based on achieving a reasonable precision in the estimate of the difference in mean number of oocytes retrieved between treatment with FE 999049 in a long GnRH agonist protocol versus treatment with FE999049 in a GnRH antagonist protocol.

In the ESTHER-1 trial, the standard deviation for the number of oocytes retrieved was 5.8 in the FE 999049 treatment group. Due to a potentially higher number of oocytes retrieved in the long agonist protocol, the standard deviation in this trial may be slightly higher. Assuming a standard deviation of 7.0, a sample size of 400 subjects (200 subjects per group) will give a 95% CI that ranges from -1.4 to +1.4 of the observed mean difference, i.e. the interval from the observed mean difference -1.4 to the observed mean difference +1.4 will with 95% probability include the true mean difference. This is regarded to be reasonably precise for describing the comparability of individualised FE 999049 dosing using the two protocols.

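### The primary and imputation models use AMH only as <15 or ≥15 pmol/L, leaving a small amount of available precision (about 0 to 3% of the SE) unused

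*SAP*

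**What the plan says.** SAP 10.2 specifies a negative binomial model with treatment, age and AMH as factors. The list reads in part "stratum (<35, 35-37, or 38-40 years), and AMH at screening (<15 pmol/L or", the other AMH level being ≥15 pmol/L. The reason given for including AMH is that "AMH at screening is additionally included as a factor since AMH is known to influence the number of oocytes retrieved". No reason is given for reducing it to two levels. Imputation step 1 says "a negative binomial regression model with age stratum and AMH at screening as factors will be fitted to data from subjects who started" treatment, separately for each protocol. Protocol 9.6.2 specifies the same two models.

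Protocol 5.1.1 has the central laboratory send the AMH concentration straight to the e-CRF, where it feeds the dose calculation. Protocol 7.3.10 requires the screening results before randomisation. A numeric value should therefore exist for every randomised woman, including those who never start FE 999049. Randomisation is stratified by centre and age only (Protocol 4.2.2). None of the supplementary analyses in SAP 10.2 uses AMH as a continuous covariate.

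**The concern.** A two-level factor treats all women below 15 pmol/L as alike, and likewise all women from 15 to the entry limit of 35. It can correct a chance difference between arms in the share of women on each side of the cut, but not a difference in AMH inside either band. Below 15 pmol/L the daily dose is the same for everyone, so any rise in response with AMH there is not offset by dosing.

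The trial is sized on confidence-interval width alone: "The trial is descriptive and does not include any hypothesis testing". Precision is what the design sets out to deliver, and a value that could sharpen it is already in the database. What is at stake is efficiency.

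**Working it through.** **1. The plan's own figure.** SAP 4.2 puts the half-width at 1.4 oocytes, in the sentence that begins "Assuming a standard deviation of 7.0, a sample size of 400 subjects (200 subjects per group) will give a 95% CI that ranges". Half-width = 1.96 × 7.0 × √(2/200) = 1.372, which rounds to 1.4. The figure reproduces, and it uses no covariate.

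**2. What the two-level factor explains.** The inputs are the ESTHER-1 results for FE 999049, all randomised women (Protocol 1.1): mean 7.5 below 15 pmol/L, 11.2 at or above it, 9.6 overall. The SD comes from SAP 4.2: "the standard deviation for the number of oocytes retrieved was 5.8 in the FE 999049 treatment group".
- Share below 15: (11.2 − 9.6)/(11.2 − 7.5) = 0.432.
- Between-band variance: 0.432 × 0.568 × 3.7² = 3.36.
- R² = 3.36/5.8² = 3.36/33.64 = 0.100.

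The triggered women give nearly the same answer. With means 8.0, 11.6 and 10.0 and SD 5.6, the share is 0.444, the between-band variance 3.20, and R² = 3.20/31.36 = 0.102. As a check on these inputs, the band SDs of 4.3 and 5.9 (Protocol synopsis) rebuild an overall SD of √(0.444 × 4.3² + 0.556 × 5.9² + 3.20) = 5.55, against the stated 5.6.

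**3. What exact AMH might explain (assumption: normal latent AMH, linear relation).** A split with share p keeps φ(z_p)²/[p(1 − p)] of the explained variance. At p = 0.43 this is 0.629, so R² for exact AMH = 0.100/0.629 = 0.159.

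| Adjustment | Half-width, SD 7.0 | Half-width, SD 5.8 |
|---|---|---|
| None | 1.372 | 1.137 |
| Two-level AMH, × √0.900 | 1.302 | 1.078 |
| Exact AMH, × √0.841 | 1.258 | 1.043 |

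At SD 7.0 the gain is about 0.04 oocyte (3.3%), equivalent to 400 × (0.900/0.841 − 1) ≈ 28 women.

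**4. Simulation of the change itself.** Step 3 does not model the cap at 35 pmol/L or test other shapes. Two negative binomial simulations did so for the factor plus log(AMH), with n = 400 and an assumed AMH distribution capped at 35. They gave these SE ratios against the planned model:

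| Assumed AMH-response shape | SE ratio |
|---|---|
| Log-linear | 0.977 and 0.985 |
| Rising to 15, then flat | 0.969 and 0.979 |
| Pure step at 15 | 1.000 and 1.000 |

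The largest gain, 3.1%, is 0.031 × 1.30 ≈ 0.04 oocyte, equivalent to 400 × (1/0.969² − 1) ≈ 26 women. The smallest is zero.

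**5. Why the factor should stay.** A further simulation (300 runs, SD 7.0) replaced the factor with log(AMH) alone. Under a pure step the half-width rose from 1.308 to 1.323. Keeping the factor and adding log(AMH) avoids that loss, as the ratio of 1.000 in step 4 shows.

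**The case against.** The strongest reply is that nothing here needs repair. Protocol and SAP agree, the model is prespecified and valid, and the half-width is about 1.30 with the planned factor against a target of 1.4 set without covariates. The cut is not arbitrary either: 15 pmol/L is where the dosing rule changes, where the subgroups divide and where ESTHER-1 reported its results. A factor needs no assumed curve and no rule for unquantifiable values. All of this stands, and it limits the point to a small efficiency gain.

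The size is also open to challenge. Above 15 pmol/L the dose per kg falls as AMH rises, and Protocol 3.5.4 aims for 8-14 oocytes in most women, so the response may be nearly flat there. ESTHER-1 had no upper AMH limit, whereas this trial excludes values above 35, so step 3 may overstate the variance that AMH explains here. The simulations apply the cap and include a flat shape, and still show a gain unless the relation is a pure step.

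A reader might infer that AMH is the strongest predictor of oocyte number. The documents say only that it has an influence, and Protocol 3.5.1 says the same of age. A reader might also infer that log(AMH) would remove all chance imbalance within bands, which is true only if that shape is right. A gain in the imputation cannot be quantified, because the documents do not give the number of women who will not start treatment.

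**Conclusion.** The point holds as a modest improvement. With the factor kept, adding log(AMH) lowers the SE of the primary comparison by about 0 to 3%, at most about 0.04 oocyte on a half-width of about 1.3, and shows no material loss in the worst case examined. The size depends on an assumed AMH distribution and assumed AMH-response shapes, since the documents report only band means and SDs. It would be wrong to conclude that the planned analysis is biased or that the trial misses its precision target: the comparison is randomised, and ±1.4 is met with or without the change.

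**What to change.** In SAP 10.2, add log(AMH) as a continuous covariate beside the <15/≥15 factor, in both the primary model and imputation step 1. Four consequences need to be written down before database lock:

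- **Protocol alignment.** Protocol 9.6.2 fixes the two-level form, and SAP sections 2 and 14 say that no protocol analysis is changed. Record the addition in section 14 as a change to Protocol 9.6.2 and amend the statement in section 2.
- **AMH subgroups.** SAP 10.2 drops AMH from these models. Specify that only the factor is dropped and log(AMH) stays.
- **Values below quantification.** There is no lower AMH limit for entry, and the LLOQ/2 rule in SAP 10.3 covers only the treatment-panel hormones. Extend it to AMH.
- **Secondary analyses.** The count analyses that reuse the primary method or model (fertilised oocytes, embryos, blastocysts, metaphase II oocytes, follicles) take the same added term. State whether the pregnancy analyses, which borrow the imputation method, follow suit.

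The cost is one more degree of freedom in the primary model, one more parameter per arm in the imputation model, the extra term in those secondary analyses, and no new data.

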## **3.5 Discussion of Overall Trial Design and Choice of Control Groups**

### **3.5.1 Trial Design**

The primary objective of the trial is to evaluate the effect of individualised FE 999049 treatment on ovarian response in a long GnRH agonist protocol versus a GnRH antagonist protocol.

This is a randomised controlled trial with a parallel group design which is preferred over a cross-over design in fertility trials. The trial will be open label as a double-blind design is not feasible due to the required GnRH agonist treatment prior to start of stimulation in a long GnRH agonist protocol. In contrast, in a GnRH antagonist protocol, the GnRH antagonist is only started during the mid-follicular phase of the stimulation period. Prior to start of stimulation in a long GnRH agonist protocol, down-regulation needs to be confirmed based on ultrasound findings, thus neither patients nor the assessors in this trial can be blinded. The lack of blinding may result in different withdrawal patterns for the two protocols. To minimise this, only subjects without strong preference for one of the protocols will be included. The trial will be a multicentre, multinational trial. This set-up ensures that the required number of subjects can be recruited within a reasonable time and also has the advantage that it should facilitate subsequent generalisation of the results.

Randomisation will be stratified by age group (<35, 35-37 and 38-40 years). Age is known to influence ovarian response, e.g. the primary endpoint, number of oocytes retrieved, as well as pregnancy endpoints such as clinical pregnancy rate and ongoing pregnancy rate. Stratification by age group will ensure that within each age group, a similar number of subjects is randomised to each protocol. This will increase the precision of the trial and facilitate separate presentations by age group. In addition, randomisation is stratified by centre as ovarian response and pregnancy outcome may differ between centres.

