### **4.2.2 Randomisation**

Randomisation may take place as soon as all eligibility criteria are met. Subjects will be randomised in a 1:1 ratio to controlled ovarian stimulation with FE 999049 in a long GnRH agonist protocol or to controlled ovarian stimulation with FE 999049 in a GnRH antagonist protocol.

Randomisation is performed centrally through the electronic case report form (e-CRF) and will be stratified by centre and according to age (<35, 35-37 and 38-40 years). The randomisation number will be allocated to the subject together with the treatment allocation. When a subject is randomised to the trial, she will always be assigned to the lowest available randomisation number. An independent statistician at the Ferring Global Biometrics Department will prepare a computer-generated randomisation list and randomisation is performed in blocks. Blocks will be maintained within centres, i.e. the randomisation will be stratified by centre. The block size will only be revealed when the trial database is declared clean and locked. An overview of recruitment will be recorded on a subject identification code list for all randomised subjects kept by the investigator.

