### **9.6.2 Primary Endpoint**

The primary endpoint will be analysed using a negative binomial regression model with protocol (long GnRH agonist protocol or GnRH antagonist protocol), age stratum (<35, 35-37, or 38-40 years), and AMH at screening (<15 pmol/L or or  $\geq$ 15 pmol/L) as factors. A logarithmic link function will be used for the mean in the model. From this model, the mean difference between the two protocols in number of oocytes retrieved will be estimated, and a 95% CI for the estimate will be calculated using the delta method. The analyses will be done using the multiple imputation method described below.

Age stratum is included as factor in the model since randomisation is stratified by age. AMH at screening is additionally included as a factor since AMH is known to influence the number of oocytes retrieved. Although randomisation is stratified by centre, centre and the interaction between centre and age stratum are not included in the model as all centres may not randomise subjects from all age strata, and therefore the inclusion of the interaction in the model is likely to give empty cells in the analysis. The potential influence of centre differences on the results will instead be investigated in a sensitivity analysis.

For subjects in the FAS who discontinue the trial after randomisation but before start of FE 999049 treatment, the number of oocytes retrieved will be imputed from subjects who started FE 999049 treatment in the same protocol, using the following multiple imputation method:

- First, a negative binomial regression model with age stratum and AMH at screening as factors will be fitted to data from subjects who started FE 999049 treatment for each protocol separately.
- In the second step, 1000 complete datasets will be constructed. For the construction of each complete dataset, a set of parameter values will be sampled from a normal distribution with characteristics determined by the estimated parameters and covariance matrix for the two models in the first step. Missing individual subject data will then be imputed from a negative binomial distribution with the sampled parameters.
- In the third step, each complete dataset will be analysed using the negative binomial regression model described in the first paragraph of this section.
- In the final step, the estimated mean differences and the standard deviations from the 1000 analyses will be combined using Rubin's formula:

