### **Supplementary analyses and descriptions for the Primary Endpoint**

The primary analysis will be repeated based on subjects in FAS that started treatment with FE 999049, i.e. without using multiple imputations (this is the same as the safety analysis set).

The potential influence of centre differences on the results for the primary endpoint will be investigated by repeating the analyses of the 1000 complete datasets generated above, with the addition of centre and the interaction between centre and age strata as factors in the model.

Additional analyses will be made for two subgroups based on AMH at screening (<15 pmol/L or  $\geq$ 15 pmol/L) and for the three age strata (<35, 35-37, or 38-40 years). These analyses will be based on the 1000 complete datasets used for the primary analyses and will use the same analysis model, except that age stratum will not be included as factor in the age strata analyses and AMH will not be included in the AMH subgroup analyses. The results of the subgroup analyses will be illustrated in a forest plot.

The distribution of number of oocytes retrieved will be described using the empirical distribution and approximated using kernel estimates.

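### The primary model leaves out centre, a randomisation stratum, for a reason that rules out only the centre-by-age interaction, and no planned analysis fits centre without that interaction

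*SAP*

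**What the plan says.** Protocol 4.2.2 keeps the randomisation blocks within centre: "Blocks will be maintained within centres, i.e. the randomisation will be stratified by centre". Protocol 3.5.1 explains why: "randomisation is stratified by centre as ovarian response and pregnancy outcome may differ between centres".

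The primary model is a negative binomial regression with protocol, age stratum and AMH group as factors. Age is there because it is a stratum: "Age stratum is included as factor in the model since randomisation is stratified by age" (SAP 10.2; protocol 9.6.2 has the same rule). Centre is also a stratum, but "centre and the interaction between centre and age stratum are not included in the model". The only reason given is that not all centres may randomise in all age strata, so that "the inclusion of the interaction in the model is likely to give empty cells in the analysis".

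Centre enters one planned analysis, the centre sensitivity analysis in protocol 9.6.2 and in the supplementary analyses of SAP 10.2. It repeats the primary analysis "with the addition of centre and the interaction between centre and age strata as factors in the model".

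**The concern.** The stated reason does not reach the term it is used to exclude. A centre main effect needs women in each centre. It does not need women in every centre-by-age cell, so a missing age stratum at a site creates no empty cell for it. By the rule applied to age, centre would be in the model.

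The planned check does not close the gap, because it fits centre only inside the model that the documents expect to be sparse. No fallback is stated if that model cannot be fitted. A reader of the results would have one analysis that ignores centre, one that may be fragile, and nothing in between.

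What is at stake is the calibration of the interval. If centres differ, stratification balances the arms within centre and lowers the true variability of the estimate. A model without centre does not see this and can report too wide an interval. In a descriptive trial sized only on interval width, that is worth checking.

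**Working it through.** **1. The plan's own figure.** With SD 7.0 and 200 per group, half-width = 1.96 × 7.0 × √(2/200) = 1.372, which rounds to the stated 1.4 (SAP 4.2). The calculation has no centre term.

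**2. Model size**, with about 15 sites and 400 women (protocol 3.2).
- Present model: 1 intercept + 1 protocol + 2 age + 1 AMH = 5 mean parameters.
- With a centre main effect: 5 + 14 = 19.
- With the interaction as well: 19 + 14 × 2 = 47.
- Centre-by-age cells: 15 × 3 = 45, averaging 400/45 = 8.9 women, or 4.4 per arm.
- Under assumed age shares from 55/28/17% to 70/20/10%, the chance of at least one empty cell is 15-69% with equal centres and 96-100% with very uneven ones. The documents' worry about the interaction is therefore well founded.

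**3. Between-centre variation.** The documents give none, so log-scale SDs of 0, 0.15 and 0.30 are assumed. For scale, take the ESTHER-1 mean of 9.6 oocytes (protocol 1.1). A centre one SD above or below has a mean of 9.6 × e^±0.15 = 11.2 or 8.3, or 9.6 × e^±0.30 = 13.0 or 7.1.

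**4. Simulation without imputation** (2,000 trials per setting). Negative binomial model with log link; difference averaged over the women in the trial; delta-method standard error.
- From the documents: 400 women, 15 centres, AMH-group means 7.5 and 11.2, total SD 5.8 (ESTHER-1) or 7.0 (planning value).
- Assumed: uneven centre sizes, ages 60/25/15% with mean ratios 1/0.92/0.85, AMH split 50/50, treatment ratio 1.1, blocks of 4 within centre and age.
- Total SD is held fixed, so centre variation sits inside it.

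HW is the mean half-width and SD(est) the empirical SD of the estimate, each without v with centre. The last column is (HW/1.96)/SD(est), from the rounded entries.

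| Total SD | Centre SD | HW | SD(est) | Model SE / true SD |
|---|---|---|---|---|
| 5.8 | 0 | 1.06 v 1.04 | 0.54 v 0.55 | 1.00 v 0.96 |
| 5.8 | 0.15 | 1.05 v 1.00 | 0.53 v 0.53 | 1.01 v 0.96 |
| 5.8 | 0.30 | 1.02 v 0.87 | 0.47 v 0.45 | 1.11 v 0.99 |
| 7.0 | 0 | 1.30 v 1.28 | 0.66 v 0.67 | 1.00 v 0.97 |
| 7.0 | 0.15 | 1.28 v 1.24 | 0.65 v 0.65 | 1.00 v 0.97 |
| 7.0 | 0.30 | 1.24 v 1.12 | 0.61 v 0.59 | 1.04 v 0.97 |

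Bias was at most 0.02 oocyte. Coverage was 94.6-96.7% without centre, 94.0-95.3% with centre (small centres pooled) and 92.8-94.0% for the planned interaction model, whose standard error was 0.93-0.95 of the true SD.

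**5. Repeat runs** (again 2,000 per setting, no imputation). Model SE over true SD, without v with centre:
- centre SD 0: 0.99-1.01 v 0.97-0.99
- centre SD 0.15: 0.99-1.02 v 0.97-0.98
- centre SD 0.30: 1.07-1.11 v 0.97-0.98

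An SD estimated from 2,000 runs has a relative error of about 1/√(2 × 2,000) = 1.6%. The two sets therefore agree within noise; the low end at centre SD 0.30 is 1.04 in one and 1.07 in the other.

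**6. Centre variation on top of SD 7.0.** Mean half-width is 1.32 v 1.28 at centre SD 0.15 and 1.40 v 1.29 at 0.30.

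**The case against.** The omission is pre-specified, identical in both documents and openly explained. Any error in the interval is towards caution, a sensitivity analysis does contain centre, and no test or margin depends on the result. All of that stands, and it limits the point to a minor one. It does not supply a reason against a centre main effect, and the planned centre analysis is the least well calibrated of the three models in step 4.

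A reader might infer three stronger things that the documents and the figures do not support.

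- *That the precision aim is missed.* The 1.4 is a rounded planning figure, not a limit each trial must meet. The present model's mean half-width is 1.02-1.30 with total SD held at the documented values, and reaches 1.40 only with large centre variation added on top. With imputation at SD 7.0 (assumed 10% and 3% non-starters), 23%, 22% and 23% of simulated trials exceed 1.4 without centre, against 17%, 12% and 5% with it at centre SD 0, 0.15 and 0.30. The fall from 23% to 17% occurs where centres do not differ at all, so part of this gap is not real precision.
- *That all the narrowing from adding centre is gain.* At centre SD 0.15 the half-width falls by 0.04-0.05 oocyte while the true SD is unchanged to two decimals. Part of the narrowing is a slightly understated standard error.
- *That protocol 3.5.1 promises precision from the centre strata.* The sentence "This will increase the precision of the trial and facilitate separate presentations by age group" is about stratification by age. For centre, the section says only that outcomes may differ.

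**Conclusion.** The point holds as a gap in reasoning and coverage: centre is omitted from the primary model on grounds that exclude only the interaction, and no planned analysis fits centre without it.

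Its numerical consequence is small. The estimate is not materially biased. For log-scale centre SDs of 0 to 0.15 the present interval is about right, with the model standard error within about 2% of the true SD. At 0.30 it is about 7-11% too wide on the repeat runs, or 4-11% on the first set. Whether centres differ that much cannot be told from the documents, so the size rests on an assumed input. Severity: minor, an optional improvement.

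**What to change.** In protocol 9.6.2 and SAP 10.2, add centre as a main effect, without the centre-by-age interaction. Pool very small centres by a rule set in advance. For example, centres with fewer than 10 randomised women form one level, which joins the smallest other centre if it is still below 10.

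- **Preferred:** put this in the primary analysis model (the third step of the imputation procedure) and keep the present model as a sensitivity analysis.
- **Minimum:** add the main-effect model as a pre-specified sensitivity analysis, beside or in place of the interaction model.

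If the primary model changes, say that the AMH and age subgroup analyses stay without centre, since they are defined as using the same model. At an assumed 15% share, the 38-40 stratum has 400 × 0.15 = 60 women, or 4 per centre. Say also whether the secondary counts that borrow the primary method follow the change.

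Cost: about 14 extra parameters, a pooling rule that would apply often (83-86% of simulated trials), and matching edits to both documents, because SAP sections 2 and 14 say that it changes nothing in the protocol analyses. No new data are needed. The standard error would be about 1-3% low, and nothing is gained if centres do not differ. With centre left out of the imputation models, simulation showed a bias of about 0.05 oocyte (Monte Carlo standard error 0.02) at centre SD 0.30, and at most about 0.02 at 0 and 0.15.
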